meta-analyses. With a final expected sample size of 215 (86, 86, 54 in Tele-Savvy (TS), attention control (AC), and usual care (UC) groups respectively), for the primary intervention test (group-by-time effect) comparing the outcomes of the three group changes from T1 to T2 to T3 (3-by-3 repeated measures design of three groups measured at three time points), at 80% power and 5% significance level, small-to-moderate effect sizes, Cohen's $f = 0.21-0.24$ may be detected for the main effects for group, time and group-by-time interaction effects (given moderate correlation between measurement pairs of $r=0.3-0.5$) (power analysis using PASS 14 Power Analysis and Sample Size Software (2015). NCSS, LLC. Kaysville, Utah, USA, ncss.com/software/pass). After adjusting for any potential group differences, the overall intervention effect of the Tele-Savvy program for the combined T1-to-T3 pre-post effects for the immediate Tele-Savvy group plus the T3-to-T5 pre-post effects from the AC and UC groups will yield a total estimated 215 subjects to perform a pre-post test to detect a small effect size of $d=0.19$ at 80% power and 5% significance level. With the pooled sample, we will be able to also test the mediating effects of mastery and self-efficacy on the Tele-Savvy program for the caregiver outcomes. As shown by Fritz and MacKinnon (2007), sample sizes of 148-196 were adequate to achieve 80% power to detect small-to-moderate effect sizes for the indirect effect of the independent variable on the dependent variable through the mediating variable considering both the Sobel test as well as percentile and bias-corrected bootstrapped approaches.¹⁰⁸ Although our analytic strategy is robust to missing data we will enroll 270 CGs (108 for TS and AC groups and 54 for UC group) per consideration 1 above (maximize accommodation) allowing for an expected 20% attrition. For the exploratory aim comparing the program's efficacy across the 3 ethnicity groups, with an expected final sample size of 215 subjects and proportions of approximately 65% Caucasian, 20% African American, 15% Hispanic, at 80% and 5% level of significance, we will be able to detect moderate effect sizes Cohen's $f=0.19-0.23$ (for 3-group by 2-time point RM-ANOVA for group, time and group-by-time effects).

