Care Recipient Mood	Neuropsychological Inventory Questionnaire	12 item inventory assessing severity of mood states or behaviors reflecting mood	Test-retest correlations between total symptom and distress scores in 15 subjects were 0.80 and 0.94, respectively (P< 0.0001 for both). ¹²¹

Data Collection. Data will be collected at baseline and at four subsequent points (months 3, 6, 9, and 12). Each data collection event will follow the same procedure used with the baseline interviews. The Navigator will establish the appointment for the Vidyo interview, and the research specialist, blinded to condition, will conduct the interview. The data collection schedule allows for a direct comparison of outcome measures between groups (at 3 and 9 months); it allows for an examination of prolonged effects (at 9 and 12 months) in the immediate participation group; and it allows for pooling of data across both groups to examine the mediating effects of mastery on distal outcomes in caregivers and PLWD and to compare effects across racial/ethnic groups. Qualitative evaluation interviews will occur at T2 and T3 for a sub-sample of immediate and T4 and T5 for a sub-sample of attention control subjects.

III. G. Variables and Measures. The table above delineates the battery of standardized instruments we will employ; these have well-established psychometric properties (reliability, validity), are used extensively with dementia caregivers, and have been used previously in the *Savvy Caregiver* trials.

As depicted in the figure below, there is a link between our theoretical model and the measures used to test it. Most data will be gathered through the regular interviews, some data will be obtained from self-reported evaluations that caregivers will complete through forms posted on the Canvas site (for example, through logs on the Canvas site in which caregivers report caregiving behaviors they have enacted). After each program, caregivers will be asked, in phone or Vidyo interviews conducted by project investigators, to evaluate the program, indicating what they did/did not like, what did/did not work, how the intervention was helpful or not, and how they would change it. Blackboard will allow us to monitor adherence, dosage and intensity of the

[figure not shown]

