Aims 1, 2 and 3 (a). Our primary aims are concerned with assessing the effect of the Tele-Savvy program for reducing or retarding the burden, depression, and anxiety of Alzheimer's family caregiving, promoting the quality of life of persons with Alzheimer's (BPSD, agitation; Quality of Life; affect), and enhancing caregiver mastery. We will employ multi-level mixed effects models (MLM) with random (participant) and fixed (cohort) effects to test linear (and non-linear) trajectories of change for the intervention groups and model group X time and group*time interactions. To compare the Tele-Savvy intervention to the attention control and usual care groups, the first 3 time points will be used to test for differences between the 3 group longitudinal trajectories. Additionally, we will combine the intervention effects for the three groups across the main 3 time points from just before receipt of the intervention to immediately after the intervention to the 1st follow-up time point (T1-to-T2-to-T3 for the immediate group and T3-to-T4-to-T5 for the attention control and usual care groups respectively). These combined time points will be referred to as cT1, cT2, cT3. If there are significant differences between or among the 3 groups at the time point immediately prior to receipt of the intervention (cT1), these "baseline" effects will be included and adjusted for in the final model. Overall time effects will be assessed as well as planned post hoc comparisons for immediate effects (cT1 to cT2), longer term effect (cT1 to cT3) and sustained effects (cT2 to cT3). Sidak Type-I error rate adjustment (which has higher power than Bonferroni) will be applied for the multiple pairwise time point comparisons.¹²² Additionally, longer term sustained effects will be captured for the immediate Tele-Savvy group using the additional follow-up times at T4 and T5 for this group. The proposed study design has the advantage of capturing 3 "baseline" time points for the wait-list attention control and usual care groups which will provide an excellent opportunity to evaluate what if any potential "placebo" effects there may be from being enrolled in this type of study.¹²³ These initial

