data captured at T1-T2-T3 for the delay group will also be used to evaluate any potential decline occurring during this time period. All model assumptions will be tested; grand mean centering used to help combat multicollinearity between variables; and standard diagnostic tests and influence statistics used to test the distributions of the residuals. MLM models utilize all available data for all participants at each time point and have the advantage of adjusting for the missing data over time, where repeated measures ANOVAs do not. Further covariate predictors of missingness over time will be included to additionally adjust for these confounders¹²⁴ To aid in final interpretation we will include the 95% confidence intervals around means by intervention group and time period. SPSS v.22 will be used for all analyses at the 5% significance level.¹²²

Aim 3(b). To test the mediating effect of mastery on Aim 1 & 2 outcomes, we will employ the PROCESS add-on module for SPSS¹²⁵ which includes performing the combined approaches of Baron and Kenney, the Sobel test, as well as semi-parametric estimation and testing of the Sobel test through bootstrapping. The focus will be on both the immediate (T2 for immediate Tele-Savvy group and T4 for attention control and usual care groups pooled together) and sustained (T3 for immediate Tele-Savvy group and T5 for attention control and usual care groups pooled together) effects of Tele-Savvy on the mediating measure of mastery on the Aim 1 and Aim 2 outcomes of caregiver burden, depression, anxiety, and dyadic relationship and PLWD BPSD, agitation, mood, and quality of life. These indirect/mediation effects will also be tested and evaluated using structural equation modeling via AMOS v.22.¹²⁶

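### The plan names only a participant random effect and specifies no within-person covariance; read literally, this assumes equal correlation between all visits

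*Combined protocol and SAP*

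**What the plan says.** Under Data Management and Analysis Plan, the paragraph on Aims 1, 2 and 3(a) specifies "multi-level mixed effects models (MLM) with random (participant) and fixed (cohort) effects", used "to test linear (and non-linear) trajectories of change for the intervention groups". Participant is the only random term named; cohort is fixed. For the randomised comparison, "the first 3 time points will be used to test for differences between the 3 group longitudinal trajectories". By the Data Collection paragraph these are baseline, month 3 and month 6, so T1-T3 spans twice the interval of T1-T2 or T2-T3.

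A second model pools the pre-to-post periods of all arms and lists "planned post hoc comparisons for immediate effects (cT1 to cT2), longer term effect (cT1 to cT3) and sustained effects (cT2 to cT3", with a Sidak adjustment.

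On model checking, the plan makes a general promise to test assumptions. The specific tools it names are centring against collinearity and "standard diagnostic tests and influence statistics used to test the distributions of the residuals". It states no covariance structure for the repeated visits, no alternative structure and no robust standard error.

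The Power Analysis and Sample Size Determination section takes its detectable effects "given moderate correlation between measurement pairs of" 0.3 to 0.5. It does not say whether that range reflects decline with time or uncertainty about one common value.

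**The concern.** A single random intercept per participant with independent residuals implies one common correlation for T1-T2, T2-T3 and T1-T3. Repeated scores on burden, depression or anxiety scales may well correlate less at 6 months than at 3. If they do, the model applies one averaged within-person variance to every change contrast: too small for the 6-month change, too large for the 3-month changes.

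The planned analyses exposed to this are:

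- **The linear trajectory over T1-T3.** With three equally spaced visits the fitted slope is half the T1-to-T3 change, so it carries the same error.
- **The pooled cT1-cT3 and cT1-cT2 comparisons.** The Sidak adjustment acts on the p-values it is given and cannot repair them.
- **The month-3 comparison between groups**, which the Data Collection paragraph singles out. Here the cost is power.

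The plan also relies on the mixed model to handle missing data, with 20% attrition expected. That protection depends partly on a suitable covariance.

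**Working it through.** **The plan's own figures.** Using a noncentral F with λ = N·f² and N = 215, 80% power at 5% gives:

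- group (df 2, 212): λ = 9.772, f = 0.213
- time (df 2, 424): λ = 9.703, f = 0.212
- group-by-time (df 4, 424): λ = 12.069, f = 0.237

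These match the stated 0.21-0.24. The paired pre-post test gives d = 0.192 against the stated 0.19. The detectable effects therefore reproduce, and the present point does not alter them.

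**Inputs.** Visits at months 0, 3 and 6 come from the plan. Arms of 86/86/43 are used because the stated 86, 86 and 54 sum to 226, not 215, and 54 × 0.8 = 43.2. The correlations by lag are assumptions: 0.5 for adjacent visits and 0.3 for T1-T3, the two ends of the plan's range. Equal variances over visits (set to 1), complete data and categorical time are also assumed.

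**Formulas.** Under a random intercept with independent residuals, the model gives every change the variance 2(1 − r̄), where r̄ is the mean pairwise correlation. The true variance for visits j and k is 2(1 − r_jk). So the SE ratio is √[(1 − r̄)/(1 − r_jk)], and the actual two-sided type I error is 2[1 − Φ(1.96 × ratio)]. The ratio does not depend on arm sizes.

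**Numbers.** r̄ = (0.5 + 0.5 + 0.3)/3 = 0.433, so the model variance is 2 × 0.567 = 1.133.

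- T1-to-T3: true variance 2 × 0.7 = 1.4; ratio √(1.133/1.4) = 0.900; type I error 7.8%; 95% interval coverage 92.2%.
- T1-to-T2: true variance 2 × 0.5 = 1.0; ratio √1.133 = 1.065; type I error 3.7%; coverage 96.3%.
- Three-arm linear slope test (2 df, critical value 5.99): exp(−5.99 × 0.809/2) = 8.8%, where 0.809 = 1.133/1.4.

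**Sensitivity to the assumed correlations.**

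| r adjacent / r T1-T3 | T1-to-T3 type I error | T1-to-T2 type I error |
|---|---|---|
| 0.5 / 0.5 | 5.0% | 5.0% |
| 0.5 / 0.4 | 6.5% | 4.3% |
| 0.3 / 0.09 | 7.1% | 4.0% |
| 0.5 / 0.3 | 7.8% | 3.7% |
| 0.5 / 0.25 | 8.4% | 3.4% |
| 0.7 / 0.49 | 9.5% | 3.0% |

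**Simulation** (8,000 trials per scenario; Tele-Savvy v attention control). At 0.5/0.3 the rejection rates were 7.6% for T1-to-T3 and 3.9% for T1-to-T2. The 4-df group-by-time test was at 5.2-6.2% across the three decay scenarios simulated (0.5/0.3, 0.5/0.25, 0.7/0.49). With an unstructured covariance, all three pairwise changes were at 4.8-5.4% in every scenario.

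**Mixed-model fits** (four REML fits at 0.5/0.3). The mean SE of the slope difference was 0.081 with a random intercept only and 0.090 with a random intercept and slope, against a true value of √[1.4 × (1/86 + 1/86)]/2 = 0.090.

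**The case against.** A reader might infer that the plan commits to equal correlation. It does not say so. It never states that the participant effect is an intercept only, and in a model of individual trajectories a participant-level slope is a natural reading. The fits above show that a random slope gives the right slope standard error. The general promise to test assumptions could also cover the covariance. This stands, and it makes the defect one of specification. It does not remove the point: no slope, structure, check or remedy is named, and a covariance chosen after seeing the data would be an undeclared choice.

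A reader might also take the 0.3-0.5 range as evidence of decline with time. The power section says nothing about lag. If the range expresses uncertainty about one common correlation, there is no error. The decline is an assumption of this review, as are equal variances; unequal variances could change the directions.

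Finally, a reader might infer that the primary result is compromised. The power section calls the group-by-time effect over three groups and three times the primary intervention test, and that 4-df test is little affected. The Tele-Savvy v attention control T1-to-T3 contrast behind the 7.8% is not itself listed in the plan. The listed pairwise time contrasts belong to the pooled analysis. Nor are the promised 95% intervals around group-by-visit means distorted under these assumptions, because they depend on total variance and not on correlation between visits.

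**Conclusion.** The concern holds as a gap in specification: participant is the only random term, and no within-person covariance is given. The literal model is a random intercept with equal correlation between visits. If correlation is 0.5 at 3 months and 0.3 at 6 months, with equal variances and complete data, the figures in the working apply: too many false positives for the 6-month change and the linear slope, and lost power for the 3-month change. For the other declining patterns tried, the 6-month type I error ranges from 6.5% to 9.5%. The primary 4-df test, the sample size and the stated detectable effects are essentially untouched. The plan should be changed because the affected slope and pooled comparisons are planned and the remedy is nearly free. The documents do not support saying that the plan forces equal correlation or that its primary test is invalid.

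**What to change.** In the T1-T3 and cT1-cT3 models, replace the participant random intercept with an unstructured covariance by visit (SPSS MIXED, REPEATED by visit, COVTYPE(UN)) and state Satterthwaite degrees of freedom. Name one fallback in advance for non-convergence: either heterogeneous Toeplitz, or a random intercept plus slope.

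For T1-T5 in the immediate arm, a more parsimonious named structure is acceptable, since an unstructured five-visit matrix needs 5 × 6/2 = 15 parameters on about 86 participants.

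The cost is a sentence or two in the analysis plan. In the three-visit models it adds four covariance parameters (six instead of two), which is negligible with about 215 participants.

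### The form of time in the T1–T3 randomised comparison is left open and no between-arm contrast at month 3 is named; if a straight line is fitted, an effect that fades by month 6 would largely be missed

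*Combined protocol and SAP*

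**What the plan says.** The analysis section (Analytic approach, Aims 1, 2 and 3 (a)) specifies multi-level mixed models "to test linear (and non-linear) trajectories of change for the intervention groups and model group X time and group*time interactions". For Tele-Savvy against attention control and usual care, "the first 3 time points will be used to test for differences between the 3 group longitudinal trajectories". The section does not state whether time is continuous or categorical, which form is confirmatory, or how one would be chosen. Its named contrasts for immediate, longer-term and sustained effects (cT1–cT2, cT1–cT3, cT2–cT3), with a Sidak adjustment, belong to the pooled pre-post analysis of all three groups and not to the randomised comparison. The same section ends by promising 95% confidence intervals for means by arm and time period, which is descriptive.

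Two other sections bear on the same test. Power Analysis and Sample Size Determination describes the primary test as a group-by-time effect in a "3-by-3 repeated measures design of three groups measured at three time points" and states that "at 80% power and 5% significance level, small-to-moderate effect sizes, Cohen's $f = 0.21-0.24$ may be detected". Data Collection says: "Data will be collected at baseline and at four subsequent points (months 3, 6, 9, and 12"; and that this schedule "allows for a direct comparison of outcome measures between groups (at 3 and 9 months".

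**The concern.** Month 3 (T2) is the first visit after the 43-day program, and the plan treats the change to that visit as the immediate effect. With three equally spaced visits, a straight-line group-by-time test compares only the change from T1 to T3, so a benefit present at T2 and gone by T3 contributes nothing to it. A categorical or quadratic model over three visits is saturated and uses T2 fully. The main randomised result can therefore depend on a choice that the plan does not record. If that choice were made after seeing the data, the type I error would also rise. Since the only named T2 contrast is a pooled pre-post one, no stated test gives a randomised answer at the visit where the data collection section promises one.

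**Working it through.** **Inputs.** Visits at months 0, 3 and 6 (Data Collection). Correlation: "given moderate correlation between measurement pairs of $r=0.3-0.5". Sample size: "With a final expected sample size of 215 (86, 86, 54 in Tele-Savvy (TS), attention control (AC), and usual care (UC) groups respectively". Those arms sum to 86 + 86 + 54 = 226, not 215. A 2:2:1 split of 215 is 86/86/43, which is assumed here. The documents give no between-arm effect or SD, so the 0.4 SD effects below are assumptions. Also assumed: Tele-Savvy differs equally from both control arms, the control arms do not change, and correlations are equal.

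**1. The plan's own figure.** Take f = √(λ/N) with N = 215, 80% power and 5% level.
- Group (2, 212 df): λ = 9.77, f = 0.213.
- Time (2, 424 df): λ = 9.70, f = 0.212.
- Group-by-time (4, 424 df): λ = 12.07, f = 0.237.

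This matches the stated 0.21–0.24. The upper end comes from the 4-df interaction, that is, visit as a category; a 2-df test gives 0.21. (The convention that builds r into f gives 0.09–0.17 and does not match.)

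**2. Weight of T2 in a slope.** For times 0, 3, 6 (mean 3), the least-squares weights are (t − 3)/Σ(t − 3)² = (−3, 0, 3)/18 = (−1/6, 0, +1/6). T2 has weight zero. The same weights result under random-intercept, random-intercept-and-slope and AR(1) covariance with complete data. It is not exact in every case: one illustrative unstructured covariance gave (−0.15, −0.03, +0.18). With 20% lost between T2 and T3 and a random intercept, the six-month slope difference picks up 0.098 (r = 0.3) to 0.105 (r = 0.5) of the T2 effect, so 0.4 SD appears as about 0.04 SD.

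**3. Power.** With Tele-Savvy shifted by effects e₁, e₂, e₃ at the three visits, the between-group factor is S = 86 × (1 − 0.4)² + 129 × (0.4)² = 30.96 + 20.64 = 51.6, where 0.4 = 86/215. Then
- λ(categorical, 4 df) = S × Σ(e − ē)² / (1 − r)
- λ(linear, 2 df) = S × (e₃ − e₁)² / 2 / (1 − r)

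Example, effects (0, 0.4, 0), r = 0.3: Σ(e − ē)² = 0.1067, so λ(categorical) = 51.6 × 0.1067/0.7 = 7.86 and λ(linear) = 0. Noncentral F with 424 denominator df gives:

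| Effect at T1, T2, T3 (SD) | Linear, r = 0.3 / 0.5 | Categorical, r = 0.3 / 0.5 |
|---|---|---|
| 0, 0.4, 0 (gone by T3) | 5% / 5% | 59% / 76% |
| 0, 0.4, 0.2 (half faded) | 17% / 23% | 46% / 61% |
| 0, 0.4, 0.4 (held) | 57% / 73% | 59% / 76% |
| 0, 0.2, 0.4 (growing) | 57% / 73% | 46% / 61% |

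With the printed 86/86/54, the first row becomes 5% against 61–77%; the conclusion does not turn on the split.

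**4. Type I error if the form were chosen from the data** (1,000,000 null draws). Counting either linear or categorical significance: 7.6%. Adding quadratic: 10.2%. Using the categorical test when the quadratic term is significant and the linear test otherwise: 7.1%.

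**The case against.** The strongest reply is that the plan does not commit to a linear slope, and that stands. A reader might infer such a commitment because linear is named first, but the sentence also allows non-linear forms. The power section's 3-by-3 test, the month 3 comparison and the means by arm and visit all lean towards visit as a category. The analysis text may be loose wording for the same test. What remains is that it does not say so.

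Second, the large losses need a fading effect, which the documents do not predict. The controlled trial of the parent program, as summarised under Savvy Caregiver Program Development and Testing, found group differences at 5 months, and a state evaluation reports gains at 5 and 12 months. This stands: the 5% figure is conditional on assumed fading. The plan does, however, set out to test sustained effects, so it treats durability as open.

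A reader might also infer that a caregiver who misses T3 has the T1–T2 change extrapolated and doubled. The stated model does not do this. With a participant random intercept, the caregiver's own T1 and T2 values enter the predicted T3 with equal weights, r/(1 + r) = 0.23 at r = 0.3 and 0.33 at r = 0.5, so that caregiver's own change adds nothing to the prediction.

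Nor is the 5% level broken as written. The inflation in step 4 requires a data-driven choice of form, which the plan neither states nor excludes.

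Finally, naming T2 and T3 contrasts without control brings its own multiplicity. Two visits by two comparators is four contrasts, and unadjusted testing gives a 16.5% chance of at least one false positive under the null (86/86/43, r = 0.5). This stands and shapes the fix.

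**Conclusion.** The point holds as a gap in pre-specification: for the main randomised comparison, neither the form of time nor a between-arm T2 contrast is fixed, and the analysis section should be brought into line with the power and data collection sections. The consequence is conditional. Under a linear form, a 0.4 SD effect gone by month 6 would be detected only at the alpha rate, and a half-faded one with 17–23% power; an effect that holds costs little. These figures rest on the assumed effects, complete data and equal correlations. Month 3 also falls roughly seven weeks after the program ends (about 91 − 43 = 48 days), so T2 is not strictly immediate. Because the plan leaves a suitable model open, the severity is below a must-fix; it is a cheap improvement with a clear gain.

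**What to change.** In Analytic approach, Aims 1, 2 and 3 (a), state that:
- the T1–T3 randomised comparison treats visit as a three-level category, with the group-by-visit interaction (the 4-df test that the power section sizes) as the confirmatory test;
- between-arm differences in change from T1 at T2 and at T3, for Tele-Savvy against each comparator, are estimated from that same model and tested only if the interaction is significant, with the Sidak adjustment the plan already uses (for four contrasts, 1 − 0.95^(1/4) = 1.27% each);
- linear or curved trajectories are descriptive only.

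This needs wording only, with no new data or visits. The cost falls on one pattern: if the effect grows in a straight line to month 6 (0.2 then 0.4 SD), the omnibus test has 46–61% power where the linear test would have 57–73%. The arm sizes in the power section should be corrected at the same time, since 86 + 86 + 54 does not give 215.

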Subject Randomization, Coordination, and Retention. Once a cohort of 15 consented subjects has been consented and interviewed, the study statistician ([name]) will use a block randomization scheme to assign equal numbers of members of the cohort to immediate Tele-Savvy or attention control or usual care wait-list participation. As the figure to the right illustrates, the three groups will each, over 12 months, get the Tele-Savvy program. Attention control program will be administered solely to participants who have been randomized to be in attention-control condition initially. Thus, participants who have been randomized to be in Tele-Savvy condition initially or to usual care will not receive attention-control intervention at 6 months post-baseline. Navigators will inform subjects of group assignment and will establish a schedule for participation. For immediate Tele-Savvy participants, start time and time of day for the videoconferences will be set. For those in attention control, start time and time of day for the videoconferences will be set likewise. For those in the usual care condition, an individual schedule of "empathetic calls" will be established. Videoconferences for both Tele-Savvy and attention control will be offered on weekdays (during business hours and evenings) and on weekends to facilitate participation for caregivers who may not be able to join videoconferences on weekdays. Caregivers who might be best served by a Saturday or an evening program will be placed into a block and randomly assigned to Tele-Savvy or attention control conditions. Caregivers for whom weekday participation is non-problematic will be allocated to conditions as described above.

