Limitations and Challenges. Our decision to limit participation to caregivers with computers and internet access is based on our pilot experience. In the ADRC pilot, we required participants to have their own computers and internet connection; we encountered very few problems. Access is not universal among caregivers, so results will not generalize to all caregivers, but, as noted, internet use in the target age groups (middle-aged and older) continues to rise.¹²⁸ We will employ easy-to-use platforms (Vidyo and Canvas) for Tele-Savvy and attention control conditions; both platforms are accessed by a simple click on an email-supplied link. Navigators can train caregivers to use Canvas and technical assistance of navigators will be provided (via phone and e-mail). A navigator will monitor all Tele-Savvy videoconferences to address any technical problems that might arise. We plan to conduct the videoconferences during weekday working hours; this may be a barrier for some eligible caregivers. To address this, we will schedule an occasional program on a weekend or in the evening. While recruitment is always a reasonable concern, our experience with the pilots provides confidence; operating with very little support, we were easily able to recruit 58 caregivers who completed the studies in the course of approximately 18 months. All of the collaborating sites were chosen because their recruitment bases are at least as strong as that at Emory. There were very few dropouts in the pilots among those who actually began the program (<10%); we have used a 25% attrition rate to be conservative in our estimates for our recruitment target.

References

1. Alzheimer's A. 2016 Alzheimer's disease facts and figures. *Alzheimers Dement*. 2016;12(4):459-509.
2. [name] K, Lewis M, Tornatore J, Sherman CW, Bremer KL. The Savvy Caregiver program: the demonstrated effectiveness of a transportable dementia caregiver psychoeducation program. *J Gerontol Nurs*. 2007;33(3):30-36.

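### Cheap precision gain: the primary T1–T3 model leaves the pre-randomisation T1 means free by arm; sharing or adjusting for T1 would cut Tele-Savvy v attention-control variance by about 29–35% (r = 0.3) or 20–25% (r = 0.5)

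*Combined protocol and SAP*

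**What the plan says.** The power section (Power Analysis and Sample Size Determination) sizes the trial "for the primary intervention test (group-by-time effect) comparing the outcomes of the three group changes from T1 to T2 to T3". It also names a main effect for group, so arm means at T1 are free. The effect sizes there are "given moderate correlation between measurement pairs of" 0.3 to 0.5.

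The analysis section (Aims 1, 2 and 3 (a)) specifies a mixed model with a random participant effect and a fixed cohort effect, and says that "the first 3 time points will be used to test for differences between the 3 group longitudinal trajectories". The only rule there on baseline scores concerns cT1 in the pooled pre/post analysis, where cT1 is T3 for the two control arms. It applies only after a significant test. The rule under Analytic approach concerns predisposing factors and is also triggered by significance.

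The section Subject Randomization, Coordination, and Retention places allocation after the baseline interview: "Once a cohort of 15 consented subjects has been consented and interviewed". It also says that caregivers best served by a Saturday or evening program "will be placed into a block and randomly assigned to Tele-Savvy or attention control conditions", whereas "Caregivers for whom weekday participation is non-problematic will be allocated to conditions as described above". Limitations and Challenges adds that "we will schedule an occasional program on a weekend or in the evening".

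**The concern.** T1 precedes allocation, so any T1 difference between Tele-Savvy and attention control is chance. A model with free T1 means estimates that difference and carries its noise into every change contrast. A model that knows the T1 means are equal, or conditions on T1, avoids this. At stake is precision from data already in hand.

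Usual care is different. Saturday/evening caregivers go to Tele-Savvy or attention control only, so usual care is drawn from weekday-available caregivers. Its T1 mean matches the other arms by design only within scheduling block. Adjusting for baseline without allowing for this would introduce a bias that the planned change contrast does not have, if the block difference is stable over time.

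**Working it through.** **Inputs.** r = 0.3–0.5, 80% power, 5% level, N = 215 with 86 in each large arm, 108 enrolled in each large arm, and 20% attrition (power section); 25% attrition (Limitations and Challenges). Assumed: compound symmetry, SD = 1 at each visit, two-sided tests (z-sum 2.80).

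**The plan's own figures.** With noncentrality N·f² and N = 215, the detectable f is 0.213 for group (2, 212 df), 0.212 for time (2, 424 df) and 0.237 for group-by-time (4, 424 df). This reproduces the stated 0.21–0.24. The pre-post figure is 2.80/√215 = 0.19, as stated. The listed arms 86 + 86 + 54 sum to 226; 86 + 86 + 43 gives 215. That discrepancy does not affect the Tele-Savvy v attention-control figures.

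**One visit, Tele-Savvy v attention control.** Enrol N per arm with n = (1 − a)N observed after T1, where a is attrition and all dropout comes before T2. Variance per arm:
- T1 means free: (1 − r²)/n + (1 − r)²/N
- T1 mean common, or T1 as covariate: (1 − r²)/n

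Reduction = 1 − 1/[1 + (1 − a)(1 − r)/(1 + r)].

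| r | a = 0 | a = 20% | a = 25% |
|---|---|---|---|
| 0.3 | 35.0% | 30.1% | 28.8% |
| 0.5 | 25.0% | 21.1% | 20.0% |
| 0.7 | 15% | 12% | – |
| 0.8 | 10% | 8% | – |

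**Detectable difference, 86 v 86, complete data.**
- r = 0.3: 2.80 × √(4 × 0.7/86) = 0.51 SD; × √0.65 = 0.41 SD.
- r = 0.5: 2.80 × √(4 × 0.5/86) = 0.43 SD; × √0.75 = 0.37 SD.

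For an assumed true effect of 0.40 SD, power rises from 60% to 79% (r = 0.3) or from 75% to 86% (r = 0.5).

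**Linear-trajectory form** (times 0, 1, 2, complete data). The slope-difference variance ratio is 2/[5 − 9r/(1 + 2r)] = 0.604 (r = 0.3) or 0.727 (r = 0.5), reductions of 40% and 27%.

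**Omnibus group-by-time test.** The covariance of the two changes is (1 − r)[[2, 1], [1, 2]]; conditional on T1 it is (1 − r)[[1 + r, r], [r, 1 + r]]. Comparing noncentralities with complete data:
- Equal effects at T2 and T3: ratio (1 + 2r)/3, a gain of 46.7% (r = 0.3) or 33.3% (r = 0.5).
- Effect at one visit only: 17.9% or 11.1%.
- Exactly opposite effects: 0%.

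With dropout before T2 the equal-effects gain is 1 − 1/[1 + 2(1 − a)(1 − r)/(1 + 2r)]. At 20% attrition this is 41% or 29%; at 25% it is 40% or 27%.

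**Usual care.** Let a share s of the Tele-Savvy arm come from the Saturday/evening block, differing by D SD at every visit. The difference from usual care due to block is then sD at T1 and at follow-up. The change contrast removes it (sD − sD = 0). A common T1 mean or a T1 covariate removes only r·sD and leaves a bias of (1 − r)·sD. The documents give neither s nor D. If 10–30% of all caregivers are in the block and the rest are allocated 2:2:1, s = (q/2)/[q/2 + 0.4(1 − q)] = 0.12 (q = 0.1) to 0.35 (q = 0.3). With D assumed at 0.2–0.5 SD, the bias runs from 0.7 × 0.122 × 0.2 = 0.02 to 0.7 × 0.349 × 0.5 = 0.12 SD at r = 0.3, and from 0.01 to 0.09 SD at r = 0.5. Block and block-by-time terms bring it to zero. For the same block shares they cost under 1 percentage point of omnibus efficiency.

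**The case against.** **The comparator is partly inferred.** The analysis section does not write out the final contrast, and Data Collection speaks of "a direct comparison of outcome measures between groups (at 3 and 9 months". Read as follow-up scores only, that comparison would gain r² with complete data: 9% (r = 0.3) or 25% (r = 0.5). This stands as an alternative reading, but the power section's wording favours change from T1.

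**The correlation may be higher.** The measures table gives test–retest values of 0.80 and 0.94 (care-recipient mood), 0.86 (caregiver reward) and 0.92 (self-rated health). These may overstate three-month correlations and do not cover burden, depression or anxiety. They do make r above 0.5 plausible for some outcomes, where the gain is much smaller.

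**Stronger claims a reader might infer.**
- That the plan ignores T1. It does not: T1 is a response. What is absent is the constraint or the covariate.
- That the planned test is invalid. Nothing here shows that.
- That the omnibus test gains 47%. That is the complete-data, equal-effects figure at r = 0.3 without block terms; the gain can be nil.
- That 20% attrition sets the floor. The document also states 25%, which gives 29% and 20%.
- That the change is free. It depends on scheduling block being an analysis variable, and no passage says that it is recorded as one.
- That the fixed cohort effect already covers the block. The text does not say that Saturday/evening caregivers form their own cohorts.

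The Design section also refers to a separate document for Amendment 8, which was not available. Whether it touches the analysis is unknown.

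**Conclusion.** The point holds as an efficiency improvement, firmest for Tele-Savvy v attention control. The headline reductions rest on compound symmetry, the planning range r = 0.3–0.5, the change-from-T1 comparator and 0–25% attrition. At r = 0.7–0.8 the reduction is 8–15% (0–20% attrition).

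The pairwise result also assumes that the Saturday/evening block is split between these two arms in the same ratio as elsewhere. The text does not state this, and a block term protects against it. For the omnibus test the gain is 0–47% (r = 0.3) or 0–33% (r = 0.5) with complete data, and about 0–41% or 0–29% with 20% dropout before T2. For usual care the change is safe only with the block handled; the size of the bias otherwise cannot be taken from the documents.

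**What to change.** In the primary T1–T3 models, do one of the following:
- treat time as categorical and omit the group term at T1, with group effects at T2 and T3 only;
- if a linear trajectory is kept, use a common T1 intercept (T1 coded 0) with group terms on the slope only;
- model T2 and T3 as responses with T1 and T1-by-time as covariates.

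Keep cohort in the model and report the unconstrained model as a sensitivity analysis. Record scheduling block before allocation and include block and block-by-time terms, or restrict usual-care contrasts to caregivers who could have been allocated to usual care.

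In the pooled cT1–cT3 model do not constrain the cT1 means: for the control arms cT1 is T3, after randomisation. Include the group term in every pooled model, not only after a significant cT1 test.

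Cost: analysis-plan wording, one recorded variable, and the small omnibus loss shown above. T1 is already collected, and SPSS mixed models can fit all these forms.
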